1. STUDY OBJECTIVES

1.1 Primary Objective

LDV/SOF for 12 weeks will have an equivalent SVR12 compared to LDV/SOF+ribavirin for 12 weeks, both initiated after liver transplant.

1.2 Secondary Objectives

Secondary objectives include the emergence and effect of NS5A and NS5B viral substitutions at baseline and in the event of relapse.

2. BACKGROUND

2.1 Rationale

Therapeutic response rates for the treatment of recurrent hepatitis C virus (HCV) after liver transplant have historically lagged behind non-transplant patients (1). While the latest studies in HCV therapy with new direct-acting antivirals (DAA) have drastically improved sustained virologic response rates (SVR) in non-transplant patients, HCV is still the most common cause of end stage liver disease (ESLD) leading to liver transplant (2,3,4,5). Although the DAAs have shown efficacy in recurrent HCV post-transplant, this is with late treatment, since preemptive therapy has not shown benefit with previous agents (6,7). An attempt at preventing recurrence by clearing the virus with SOF and RBV prior to transplant has shown encouraging preliminary results in patients who had HCV RNA undetectability for ≥ 30 days, however this was in well-compensated cirrhotics ($CTP \leq 7$) with concomitant HCC (8). Due to the poor tolerability of RBV in patients with more advanced cirrhosis, it is unknown if this regimen would have external validity to the overall HCV population awaiting liver transplant. Also complicating the reproducibility of this data is the unpredictable timing of liver transplant surgery.

[figure not shown]
Preliminary results of the ongoing SOLAR-1 study have shown excellent sustained virologic response (SVR) rates with 12 weeks of therapy both pre and post-transplant, when utilizing a regimen of LDV/SOF and RBV (9). However, this is with a regimen that includes an antiviral with poor tolerability post-transplant, ribavirin.

The predominant remaining questions for post-transplant treatment of HCV in the DAA era are whether a ribavirin-free regimen is possible and whether pre-emptive treatment is now a potential option to prevent long-term damage to the allograft.

These questions require formal testing in a clinical trial conducted in transplant centers.

2.2 Supporting Data

SOLAR-1 – Phase III randomized, open-label study including post-transplant (Cohort B) (ongoing)

a. Results

Post-transplant F0-F3, CPT A/B/C (cohort B)

- i. N=223, 12 vs 24 wks of LDV/SOF+riba (weight-based in F0-F3 and CPT A, 600mg titrated up in CPT B and C)
- ii. Median time since transplant 2.9-8.1 yrs depending on arm
- iii. SVR rate
 1. F0-F3 96-98% (N=111)
 2. CPT A 96-96% (N=51)
 3. CPT B 85-83% (N=44)
 4. CPT C (N=8) (only 9 pts in this arm, 1 has not reached SVR end-point timeframe) 60-67%

Risks of therapy

	HARVONI 8 weeks N=215	HARVONI 12 weeks N=539	HARVONI 24 weeks N=326
Fatigue	16%	13%	18%
Headache	11%	14%	17%
Nausea	6%	7%	9%
Diarrhea	4%	3%	7%
Insomnia	3%	5%	6%
Bilirubin elevations 1.5x ULN	3%	<1%	2%
Lipase elevations 3x ULN	<1%	2%	3%

3. STUDY DESIGN

Multi-center, prospective, randomized, open-label, pilot study

ARM 1: LDV/SOF x 12 weeks

ARM 2: LDV/SOF + RBV x 12 weeks

Number subjects:

Multi-center

50 subjects, with 25 subjects in each arm

4. SELECTION AND ENROLLMENT OF SUBJECTS

4.1 Inclusion Criteria

- a. At least 18 years of age
- b. Signed informed consent
- c. History of HCV genotype 1 or 4
- d. No clinically significant abnormalities or changes on EKG
- e. Randomization post orthotopic liver transplant
- f. Detectable HCV RNA at baseline
- g. Creatinine Clearance of at least 40ml/min using the Cockcroft Gault equation
- h. Negative pregnancy test for female subjects of child bearing potential within 48 hours of randomization

Subjects of reproductive potential agree to use (or have their partner use) two effective contraception methods through 6 weeks following completion of intervention. Subjects who are not of reproductive potential, not sexually active, whose current partner(s) is not of reproductive potential, or whose sexual activity is exclusively homosexual are eligible without requiring the use of contraception.

4.2 Exclusion Criteria

- a. Pregnant or nursing female, or male with a pregnant female partner
- b. A condition or disorder that, in the opinion of the investigator, may adversely affect the outcome of the study or the safety of the subject
- c. Stomach disorder that could interfere with the absorption of study drug
- d. Co-infected with HBV or HIV
- e. Allergic to sofosbuvir or ledipasvir
- f. History of completed treatment with a Nonstructural Protein 5A (NS5a) inhibitor

- g. Participation in a clinical study with an investigational drug or biologic within 30 days of randomization
- h. Fibrosing cholestatic hepatitis
- i. Amiodarone use within 6 months of randomization
- j. Unwilling/unable to stop taking any of the prohibited medications (Section 5.2)
- k. Total bilirubin >10mg/dL
- l. Alanine transaminase (ALT), aspartate transaminase (AST), or alkaline phosphatase (ALP) $\geq 10x$ ULN
- m. Serum sodium < 125mmol/L
- n. Platelet count of ≤ 30 k/mm³
- o. Hemoglobin < 10g/dL
- p. Allergic to or intolerant of ribavirin
- q. Within 1 year of transplant AND history of Hepatocellular Carcinoma (HCC) with tumor burden outside of the Milan Criteria (See Appendix II) prior to transplant
- r. History of significant or unstable cardiac disease
- s. Recipients of an allograft from a donor that was infected with HCV with an unknown genotype or non-genotype 1 or 4 unless the recipient is demonstrated to have only genotype 1 or 4 HCV replication post-transplant
- t. Childs Turcotte Pugh (CTP) B or C

4.3 Study Enrollment Procedures

- 4.3.1 Subject Identification/Recruitment: Members of the research team will identify potentially eligible patients who are undergoing liver transplantation or have previously undergone liver transplantation that are infected with Hepatitis C. An initial evaluation of existing patient information may be performed to determine potential eligibility. This initial review may be performed prior to consent; however no protocol driven tests or procedures may be performed until signed informed consent has been obtained.
- 4.3.2 Informed Consent: Authorized personnel will approach patients to explain the study and offer the opportunity to participate in the study. The personnel who will obtain

consent will have completed Human Subjects Protection Training. This research study will be explained in lay terms to each potential research participant. In compliance with the informed consent process outlined in CFR Title 21 Part 50, the authorized personnel will conduct a face-to-face meeting with the study candidate to review all of the required elements of informed consent. The potential study participant will sign an informed consent form before undergoing any screening study procedures. The original consent form will be kept with the subject's file in the office. A copy of the consent will be given to the patient and another copy will be put in his/her chart. At the time of consent, patients will be assured that their care will not be affected in any way if they choose not to participate in the study. Patients will also be reminded that it is their right to withdraw their participation in the study at any time.

- 4.3.3 Enrollment: Patients who give informed consent to study participation will go on to complete baseline procedures necessary to determine eligibility for randomization. Once deemed eligible for the study according to the inclusion/exclusion criteria, the patient will be enrolled as study subject in the WebDCUTM clinical trial management system (CTMS). Information to be entered upon enrollment includes demographic information and date of transplant surgery. Enrolled subjects will be randomized to one of the treatment arms. The study team will receive the randomization assignment from WebDCUTM.

5. STUDY INTERVENTIONS

5.1 Interventions, Administration, and Duration

i. **SOF/LDV administration**

At the time of randomization, all subjects will be initiated on SOF/LDV 400mg/90mg enterally daily either with food or on an empty stomach. This medication will be administered predominantly outpatient, although it may be started or continued on both general hospital floors as well as the ICU. The medication will be continued for 12 weeks in both arms.

ii. **Ribavirin administration**

At the time of randomization, subjects in Arm 2 will be initiated on the appropriate weight-based dose to be taken with food. Subjects < 75kg will be initiated on RBV 400mg enterally in the morning (QAM) and 600mg enterally at night (QPM). Subjects \geq 75kg will be initiated on RBV 600mg enterally in the morning and night (BID).

This medication will be administered predominantly outpatient, although it may be started or continued on both general hospital floors as well as the ICU.

Ribavirin dosing may be adjusted as medically required for toxicity (see section iii).

iii. **Dosage adjustment of ribavirin**

Laboratory Abnormality	Reduction in current ribavirin dose
Hgb 8.5 to <10 g/dL and/or decrease by > 2 g/dL within 4 weeks	1. Decrease dose to 600mg daily (200mg QAM, 400mg QPM) 2. If Hgb < 12 g/dL despite 4 weeks of dose reduction in subjects with a history of stable cardiac disease, discontinue ribavirin
Hgb <8.5 g/dL	Discontinue ribavirin
WBC <1000 mm³ and/or ANC <500 mm³	Discontinue ribavirin
Platelets < 25 k/mm³	Discontinue ribavirin
eGFR 30-50 ml/min	Alternating doses, 200mg and 400mg every other day

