Gastrointestinal disorders	Diarrhea	1 - Increase of < 4 stools per day over baseline; mild increase in ostomy output compared to baseline	Grade 3 if requested by study participant, treatment-resistant or recurrent; Grade 4 or 5	Intervention can be withheld for up to 5 days. If there is no resolution, the case will be discussed with the medical monitor and the intervention may be discontinued. Grade 5: Intervention will be permanently discontinued
		2 - Increase of 4-6 stools per day over baseline; moderate increase in ostomy output compared to baseline		
		3 - Increase of ≥ 7 stools per day over baseline; incontinence; hospitalization indicated; severe increase in ostomy output compared to baseline; limiting self care ADL		
		4 - Life-threatening consequences; urgent intervention indicated		
		5 - Death		
Psychiatric disorders	Insomnia	1 - Mild difficulty falling asleep, staying asleep or waking up early	If requested by study participant	Intervention can be withheld for up to 5 days. If there is no resolution, the case will be discussed with the medical monitor and the intervention may be discontinued.
		2 - Moderate difficulty falling asleep, staying asleep or waking up early		
		3 - Severe difficulty in falling asleep, staying asleep or waking up early		
Musculoskeletal and connective tissue disorders	Arthralgia	1 - Mild pain	Grade 3 or if requested by study participant	Intervention can be withheld for up to 5 days. If there is no resolution, the case will be discussed with the medical monitor and the intervention may be discontinued.
		2 - Moderate pain; limiting instrumental ADL		
		3 - Severe pain; limiting self care ADL		

Renal and urinary disorders	Chronic kidney disease	1 - CrCl < LLN-60ml/min/1.73m ² ; proteinuria 2+ present; urine protein/creatinine > 0.5	Grade 2	Sofosbuvir/Ledipasvir to be held if CrCl <40ml/min/1.73m ² . Intervention can be withheld for up to 5 days. If there is no resolution, the case will be discussed with the medical monitor and the intervention may be discontinued. Ribavirin dose should be reduced to alternating doses of 200mg and 400mg every other day if CrCl 30-50ml/min/1.73m ² Interventions can be withheld for up to 5 days. If there is no resolution, the case will be discussed with the medical monitor and the intervention may be discontinued. Grade 5: Intervention will be permanently discontinued
		2 - CrCl 59-30m/min/1.73m ²		
		3 - CrCl 29-15ml/min/1.73m ²	Grade 3-5	
		4 - < 15ml/min/1.73m ² ; dialysis indicated		

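### Ribavirin starts by weight alone, so an eligible Arm 2 subject already in the protocol's renal-reduction range is directed to 3.3 to 4.0 times its renal dose, unless the site acts on the baseline value

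*Combined protocol and SAP*

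**What the plan says.** The renal entry limit in Section 4.1(g) is "Creatinine Clearance of at least 40ml/min using the Cockcroft Gault equation". The exclusion list in Section 4.2 adds no renal criterion.

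Section 5.1.ii sets the start of ribavirin at randomization: "subjects in Arm 2 will be initiated on the appropriate weight-based dose to be taken with food". Weight is the only factor. Below 75 kg the dose is 400 mg in the morning and 600 mg at night; at 75 kg or above it is 600 mg twice a day. The one route to another dose that 5.1.ii mentions is "Ribavirin dosing may be adjusted as medically required for toxicity (see section iii".

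That table, in 5.1.iii, has an action column headed "Reduction in current ribavirin dose". Its renal row is triggered at "eGFR 30-50 ml/min", and the action is "Alternating doses, 200mg and 400mg every other day". The chronic kidney disease row of Section 7, which deals with adverse experiences, repeats the rule: "Ribavirin dose should be reduced to alternating doses of 200mg and 400mg every other day if CrCl 30-50ml/min", in units per 1.73 m².

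The Schedule of Evaluations (6.1) requires laboratory assessments at baseline and then at Weeks 4, 8 and 12. Under 6.2.1 the baseline tests may be done up to 14 days before randomization.

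**The concern.** The entry limit of 40 lies inside the range, 30 to 50, in which the protocol itself calls for a reduced ribavirin dose. A subject can therefore be eligible, be started on the full weight-based dose, and already meet the protocol's condition for a much smaller one. No section says which instruction prevails at the first dose.

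This looks like an oversight. Where other rows of the 5.1.iii table share a measure with an entry criterion, entry keeps subjects out of the absolute trigger range. Hemoglobin below 10 g/dL is excluded, and the hemoglobin triggers lie below 10. Platelets of 30 k/mm³ or less are excluded, and the trigger is below 25. White cells and neutrophils have no entry limit. Only the renal limit falls inside its own trigger range.

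Two things are at stake. The first is the safety of the individual subject: the rationale in Section 2.1 itself describes ribavirin as poorly tolerated after transplant. The second is consistency. Ribavirin is the only planned difference between the arms, and two careful sites could start the same patient on 300 mg/day or 1200 mg/day. Dose reduction for intolerance is also a safety outcome (9.2.3 and 9.7.1). A reduction that was foreseeable at baseline could be counted as intolerance at one site and not at another.

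**Working it through.** The protocol gives the doses but no ratio, so there is no stated figure to reproduce.

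**Inputs**
- Starting dose (5.1.ii): 400 + 600 = 1000 mg/day below 75 kg; 600 + 600 = 1200 mg/day at 75 kg or above.
- Renal dose (5.1.iii and Section 7), read as 200 mg one day and 400 mg the next: (200 + 400) / 2 = 300 mg/day on average.
- Entry limit (4.1(g)): 40 ml/min. Renal range: 30 to 50.

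**Overlap.** On the Cockcroft-Gault scale, the eligible part of the range is 40 to 50 ml/min. The three places do not use one scale, however: 4.1(g) uses Cockcroft-Gault in ml/min, 5.1.iii uses eGFR in ml/min with no equation named, and Section 7 uses clearance per 1.73 m². A subject at Cockcroft-Gault 40 to 50 need not meet every trigger, and an eligible subject could have an eGFR anywhere in 30 to 50.

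**Ratio of starting dose to renal dose**
- Below 75 kg: 1000 / 300 = 3.3
- 75 kg or above: 1200 / 300 = 4.0

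**Difference per day until the renal row is applied**
- Below 75 kg: 1000 − 300 = 700 mg
- 75 kg or above: 1200 − 300 = 900 mg

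**Sensitivity to the reading of the renal dose.** If the words meant drug on every second day only, the mean would be (200 + 400) / 4 = 150 mg/day, and the ratios 1000 / 150 = 6.7 and 1200 / 150 = 8.0. Day-by-day alternation is the natural reading, and it gives the smaller ratios, which are used here.

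**Does the text direct a reduced start?**
- 5.1.ii makes the weight-based start an instruction, and the word *appropriate* there refers to weight.
- Adjustment is permissive and is tied to toxicity, which cannot be present before the first dose.
- The table heading speaks of a dose already being taken.
- The Section 7 row governs adverse experiences, not baseline status.

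None of these forbids a reduced start, but none directs it.

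**The case against.** The strongest reply is that the protocol already supplies both the dose and the trigger. The 5.1.iii renal row is an absolute value. It asks for no fall from baseline, no time on drug and no attribution to ribavirin, whereas the first hemoglobin row includes a change criterion. Eligibility cannot be judged without a creatinine clearance, so the site knows the subject's renal function before the first dose. On a literal reading the row can be met on day 0, when the current dose is the one just assigned by weight. The investigator may also exclude a patient on safety grounds under 4.2(b).

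Much of this stands. A site may apply 5.1.iii at once, so the excess is conditional on what the site does. What does not stand is that the text settles the matter. A site that follows the starting instruction as written gives the full dose. A site that lowers it must read a toxicity rule as a starting rule, while Section 11.1 discourages departures from the protocol except to remove an immediate hazard.

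A reader might infer that affected subjects would receive the full dose for four weeks, because no laboratory assessment is required between baseline and Week 4. The documents do not support that as an expected exposure: it assumes that the site ignores a value it already holds and does no unscheduled test.

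A reader might also infer from the per-1.73 m² units that some subjects enter already below the Section 7 threshold for holding LDV/SOF. That needs body sizes and an indexing rule that the documents do not give, and it is not claimed.

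**Conclusion.** The starting rule is wrong as written for one group: eligible Arm 2 subjects whose baseline renal value already lies in the 30 to 50 range. It directs them to 3.3 times (below 75 kg) or 4.0 times (75 kg or above) the dose that the protocol sets for that renal function, unless the site chooses to apply 5.1.iii to the baseline value. The arithmetic rests only on doses in the protocol and on the day-by-day reading of the alternating dose.

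The documents give no baseline renal distribution, so the number affected may be anything from none to all 25 Arm 2 subjects, and the duration depends on the site. It would be tempting to conclude that the trial's efficacy estimate is compromised. Nothing in the documents supports that, and no effect on SVR12, sample size or power is claimed. The point is a foreseeable dosing conflict that can be removed before the first dose.

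**What to change.** Add to 5.1.ii: *Arm 2 subjects with baseline Cockcroft-Gault clearance of 50 ml/min or below start ribavirin at alternating 200 mg and 400 mg daily doses; this is not counted as a dose reduction for intolerance.* In the 5.1.iii renal row, replace eGFR with the same Cockcroft-Gault measure in ml/min, so that entry, start and later adjustment use one scale. The change of measure may alter which subjects that row catches.

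A shorter alternative, stating that 5.1.iii also applies to baseline values, would close the gap at the start. It would leave the eGFR equation unnamed and the counting of dose reductions unsettled.

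The cost is a dosing amendment, with local IRB approval at each participating institution (11.1) and updated site instructions. The baseline value is already collected, so no visit, test or subject is added and the sample size does not change.

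### The hemoglobin and eGFR rows of the ribavirin table give different doses to a subject who meets both, and a subject already on the renal dose has no usable anemia step

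*Combined protocol and SAP*

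**What the plan says.** Section 5.1.ii sets the Arm 2 starting dose by weight. For the lighter group: "Subjects < 75kg will be initiated on RBV 400mg enterally in the morning (QAM) and 600mg enterally at night (QPM"). Subjects at or above "75kg will be initiated on RBV 600mg enterally in the morning and night (BID").

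Section 5.1.iii then gives a table of adjustments under the column heading "Reduction in current ribavirin dose". Two of its rows matter here:

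- The hemoglobin row is triggered by "Hgb 8.5 to <10 g/dL and/or decrease by > 2 g/dL within 4 weeks". Its first step is "Decrease dose to 600mg daily (200mg QAM, 400mg QPM").
- The renal row is triggered by "eGFR 30-50 ml/min". Its instruction is "Alternating doses, 200mg and 400mg every other day".

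The chronic kidney disease entry in Section 7 repeats the renal instruction: "Ribavirin dose should be reduced to alternating doses of 200mg and 400mg every other day if CrCl 30-50ml/min". The Section 7 entries for Grade 2 anemia and Grade 2 hemolysis give no dose of their own and refer the site to Section 5.1.iii. The general clause in Section 5.1.ii that allows adjustment for toxicity refers to that same table.

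**The concern.** The hemoglobin row gives an absolute target, whatever dose the subject is taking. That works from the starting doses, which are well above 600 mg/day. It does not work from the renal dose, which is below it. The table does not say what a site should do when both triggers are present, or when anemia appears in a subject whose dose was already lowered for renal function.

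The first matter at stake is safety: a subject with moderate anemia and reduced renal function is one for whom sites need a clear instruction. The second is consistency: ribavirin is the only planned difference between the arms, and two sites could handle identical laboratory values differently. The third is coding: dose reduction is a named safety outcome in Sections 9.2.3 and 9.7.1, and the protocol does not say what counts as the anemia reduction for a subject already below the target. Step 2 of the hemoglobin row, for subjects with stable cardiac disease, counts four weeks of dose reduction, and it is not clear when that count starts for a subject already on the renal dose.

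**Working it through.** **Inputs.** Starting doses: Section 5.1.ii. Hemoglobin target and renal dose: Section 5.1.iii, with the renal dose repeated in Section 7. Entry limits: Sections 4.1.g and 4.2.o.

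**The plan's own figure.** 200 mg in the morning + 400 mg at night = 600 mg/day. This reproduces.

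**Starting doses.** Below 75 kg: 400 + 600 = 1000 mg/day. At 75 kg or above: 600 + 600 = 1200 mg/day.

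**Mean renal dose.** If a dose is taken every day, alternating 200 and 400 mg: (200 + 400) / 2 = 300 mg/day.

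**Each row applied to each possible current dose:**

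| Current dose (mg/day) | Hemoglobin row: 600 mg/day | Renal row: mean 300 mg/day |
|---|---|---|
| 1000 | 600/1000 = 60% of current | 300/1000 = 30% of current |
| 1200 | 600/1200 = 50% of current | 300/1200 = 25% of current |
| 600 (after the hemoglobin step) | no change | 300/600 = 50% of current |
| 300 (after the renal step) | 600/300 = 200% of current | no change |

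The first two lines show the conflict at the starting dose. Both rows are true reductions, but they differ by 600 − 300 = 300 mg/day, and nothing says how they combine. The last two lines show that order matters. Anemia followed by renal decline gives a further reduction, as the heading promises. Renal decline followed by anemia gives a target above the current average dose.

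**What is left for the subject on the renal dose.** The table's other hemoglobin rule is discontinuation below 8.5 g/dL. It does not reach the band from 8.5 to just under 10, or a fall of more than 2 g/dL that ends at 8.5 or above. Section 7 refers back to the table, so it does not fill the gap.

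**Can the overlap occur?** Section 4.1.g admits creatinine clearance of 40 ml/min or more, so a subject at 40 to 50 can enter already within the renal row's range. Section 4.2.o excludes only hemoglobin below 10 g/dL, so a subject entering at 10 meets the hemoglobin row after any fall that stays at or above 8.5. This treats the Cockcroft-Gault clearance used for entry and the eGFR used in the table as comparable; Section 7 states the same 30 to 50 range in terms of clearance.

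**The case against.** The strongest reply is that the protocol nowhere tells a site to raise ribavirin. A reader might infer that an anemic subject on the renal dose is ordered to double it. The documents do not support that. The row's verb is to decrease, the column heading speaks of reduction, and a mean of 300 mg/day cannot be decreased to 600. The renal instruction, stated in both Section 5.1.iii and Section 7, also continues to apply while renal function stays in range, and nothing says anemia lifts it. This part of the reply stands: the defect is a contradiction and a gap, not an instruction to increase.

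Three other stronger readings also fail:

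- **A doubling on every day.** The factor of 2 holds only for the average daily dose. Against single days it is 600/400 = 1.5 or 600/200 = 3.
- **A fourfold difference.** This needs the renal row to mean a dose only every second day, so (200 + 400) / 4 = 150 mg/day and 600/150 = 4. That strains the words about alternating doses. It is a reason to clarify the phrase, not a measure of the problem.
- **A disagreement between the two sections on the renal dose.** There is none; they give the same ribavirin dose.

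The reply also points to handling elsewhere. The kidney entry in Section 7 holds LDV/SOF when clearance is below 40 and brings in the medical monitor if there is no resolution, so a subject at 30 to 39 would already come under discussion. This narrows the unaddressed overlap mainly to 40 to 50. It does not close it, because 40 to 50 is the part of the range open at entry, and the entry does not address concurrent anemia.

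**Conclusion.** The concern holds as an unresolved conflict between two rows of one table. A subject on a starting dose who meets both rows has two reductions that differ by 300 mg/day on average. A subject already on the renal dose has a hemoglobin step whose target is twice the current average, contrary to the column heading, and so has no usable anemia step short of discontinuation below 8.5 g/dL. These figures assume that the renal dose is taken daily.

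Only Arm 2 subjects who meet both triggers are affected. The documents give no basis for a count; with 25 subjects planned in the arm it may be zero. A reader might infer damage to the SVR12 comparison, but nothing in the documents shows that. Section 9.4.2 describes intent-to-treat estimates without power for formal testing, and ambiguity in a few ribavirin doses has no demonstrated effect on them. The case for acting rests on safety, consistent conduct across sites and coherent coding of dose reductions. On those grounds the protocol should be clarified.

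**What to change.** The sponsor's clinicians should reconcile the hemoglobin and eGFR rows of Section 5.1.iii for subjects who meet both, whether at the same time or one after the other, so that the hemoglobin row agrees with its column heading. The Section 7 entries for anemia, hemolysis and chronic kidney disease should be brought into line with the result. The text should also say whether the alternating renal dose is taken daily or only on alternate days, and when the four-week count in step 2 of the hemoglobin row begins for a subject already on the renal dose. No dose or clinical rule is proposed here; those are for the sponsor's clinicians.

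The cost is a short clarification under the table with matching cross-references in Section 7. It adds no patients, visits or procedures and does not change the sample size.
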